## **STUDY SUMMARY**

Full title		The impact of COVID-19 pandemic on the provision, practice and outcomes of vascular surgery			
Short title	COVER	COVER			
Aim	Assess the impact of COVII	Assess the impact of COVID-19 on vascular surgery			
Design	Multicentre Cohort Study	Multicentre Cohort Study			
Participants	•	All patients with a vascular pathology idenfied and treated during the COVID-19 pandemic			
Sample size	200 participants - ESTIMAT	200 participants - ESTIMATED			
Planned project period	24 months - ESTIMATED	24 months - ESTIMATED			
	Objectives	Outcome Measures			
Primary	Assess how the COVID-19 pandemic has changed the provision of vascular services in the UK	Collect data regarding the types of procedures performed in vascular units.			
Secondary	Assess how the COVID-19	Collect data regarding			

Key Words: Coronavirus, Cohort study, Outcomes, Vascular, Surgery

## **SCHEDULE OF EVENTS**

## Table 1: Schedule of Events

The duration of this project will depend on the duration of the COVID19 pandemic

We aim to capture information throughout the pandemic and then for 12 months after the pandemic has ended (i.e. Tier 3 outcomes for 12 months).

Procedure	Screening	Baseline	3 months	6 months	12 months
Eligibility assessment	X	X			
Informed consent (Tier 2 only)		X			
Demographic data (DOB, sex)		X			
Stored only locally		^			
Relevant clinical history		X			
Current medications		X			
Assessment of outcomes i.e. death or		X	×	~	V
amputation or stroke		^	^	^	^
End of study		X			X

# LIST OF ABBREVIATIONS

AAA	Abdominal Aortic Aneurysm
AR	Adverse reaction
CI	Chief Investigator
CRF	Case Report Form
CRO	Contract Research Organisation
EC	Ethics Committee (see REC)
EVAR	Endovascular Aneurysm Repair
GCP	Good Clinical Practice
GP	General Practitioner
HRA	Health Research Authority
IB	Investigators Brochure
ICF	Informed Consent Form
ICH	International Conference of Harmonisation
IMP	Investigational Medicinal Products
ISF	Investigator Site File
NHS	National Health Service
NICE	National Institute for Health and Care Excellence
NRES	National Research Ethics Service
OAR	Open Aneurysm Repair
PI	Principal Investigator
PIL/S	Participant/ Patient Information Leaflet/Sheet
R&D	NHS Trust R&D Department
REC	Research Ethics Committee
SMF	Study Master File
SOP	Standard Operating Procedure
SpR	Surgical Registrar

#### STUDY PROTOCOL

The impact of COVID-19 pandemic on the provision, practice and outcomes of vascular surgery

#### 1. INTRODUCTION

The COVID-19 pandemic has already had a significant impact on worldwide healthcare systems. There is an urgent need to quantify the specific impact on the provision of vascular and endovascular surgery and the adjustments made to standard vascular practice in light of the pandemic. Reasons for this include:

- 1. The Vascular Society of Great Britain and Ireland (VSGBI) has released a statement with guidance for altering clinical management of patients with vascular diseases, due to the limitations on healthcare resources and capacity. Worldwide, centres are doing the same as the pandemic has progressed. For most, this involves offering fewer vascular interventions alongside postponing any non-urgent interventions and treatments. Assessing how centres implement the VSGBI recommendations and manage patients in the context of the considerable changes to available resources is imperative during this outbreak and any future major incidents.
- 2. An international snapshot of how each unit is changing their practice at the patient level in response to the pandemic will ensure that centres across the UK and the world are aware of global practice to unify their planning during the pandemic.
- 3. The impact of cancelling elective work, deferring all but the most urgent and emergency surgery and proceeding to amputation without complex revascularisation, will be felt almost immediately. However, we must anticipate the volume of work that, after resuming a normal service again, will need to be managed on top of standard case volume. Knowing the impact of the pandemic on the numbers of cases deferred and how their overall care has changed is imperative in order to plan future vascular care both nationally and internationally.

This project is a three-tiered study designed to answer these questions. We aim to capture global data on vascular practice(s) during the pandemic; how this evolves over time; and to understand the impact on outcomes in the short and medium-term.

This project will be led by the **Vascular and Endovascular Research Network (VERN)**. This is an established vascular research collaborative, which has previously designed and delivered several similar projects across the UK and internationally. Details about VERN, including the membership of its executive committee, can be found online: www.vascular-research.net (updated regularly). This project is also formally supported by the VSGBI, the British Society for Endovascular Therapy, and the Rouleaux Club (the UK body representing vascular surgery trainees).

#### 2. RATIONALE

## 2.1 Aims and hypothesis

This project is a three-tiered study designed to answer the questions covered in the Introduction i.e. assess the impact. We aim to capture global data on vascular practice(s) during the pandemic; how this evolves over time; and to understand the impact on outcomes in the short and medium-term.

## 2.2 Justification

This project will provide clinicians assessing and treating patients with vascular disease an understanding of the impact of the COVID19 pandemic in order to plan patients' care accordingly in the future and also be prepared for future similar issues.

## 2.3 Assessment and management of risk

This project will have no impact on patients' journey in the NHS or any other healthcare provider.

## 3. OBJECTIVES AND OUTCOME MEASURES/ENDPOINTS

## 3.1 **Primary objective**

The main objective of this project is to understand and evaluate the impact of the COVID-19 pandemic on global vascular practice and the effect on outcomes for patients presenting / receiving treatment during the pandemic.

- **P** Population (patients) All patients with a vascular pathology.
- I Intervention NONE. Observational study.
- **C** Comparison group NONE. Observational study.
- Outcome of interest Tier 1: state of vascular services per centre weekly; Tier 2: procedures performed in each centre; Tier 3: assessment of longer-term outcomes.
- **T** Time end of study 12 months after the end of the COVID19 pandemic.

Details regarding all endpoints are listed under STUDY PROCEDURES under each Tier of this project.

#### 4. STUDY DESIGN

## Three tiered project.

**Tier 1** does not constitute research (remote anonymised survey of healthcare professionals)

**Tier 2** and **3** constitute research and are described in full detail under STUDY PROCEDURES (see below). These are observational studies within.

#### 5. STUDY SETTING

This is a multicentre observational study in NHS sites across the UK, including England, Scotland, and Wales.

All NHS sites which provide regular care to vascular patients are eligible (secondary care).

This study will have NO impact on regular NHS care and will only documents patients' NHS care pathways.

#### 6. ELIGIBILITY CRITERIA

All patients with vascular diseases are eligible to take part, as long as they have received assessment or treatment for a vascular problem in an NHS secondary care vascular unit.

### 6.1 Inclusion criteria

Vascular pathology including: aneurysmal disease, stroke, peripheral arterial disease, venous disease.

#### 6.1 Exclusion criteria

Only adult patients will be eligible to consent (tier 2 only) and take part.

## 7. STUDY PROCEDURES

This project will consist of THREE stages ("TIERS").

Tier 1 is an online survey of experts in vascular care (anonymised) and does not constitute research. Consent for this is not necessary.

Patients (for Tiers 2 and 3) will be identified prospectively:

At the time of surgery

At the time of referral to the vascular on-call team.

These constitute research.

## Tier 1 - Changes to vascular unit level clinical processes

## **Primary objective**

To objectively capture the changes made to the structure and delivery of vascular surgery at unit level throughout the COVID-19 pandemic, and compare it to the guidance provided by the VSGBI as well as other national/international committees (e.g. the Society for Vascular Surgery, the European Society for Vascular Surgery).

#### **Methods**

The Tier 1 "service evaluation study" will be circulated to all interested centres and data collected (remotely/online) at the start of COVER. The aim is to identify changes to the routine or standard vascular service structure. This will be conducted at roll-out and upon each centre registering to participate in the overall study bundle. This survey will be repeated at regular intervals to document ongoing changes, in response to the changing circumstances. These intervals will vary depending on how the pandemic progresses internationally. Collaborators will be updated at least once weekly. It is expected that the responses will reflect the unit practice as a whole and should therefore be a unified unit level response approved by the centre or centre lead.

### **Outcomes**

#### **Primary outcome:**

To document changes to structure and processes within the vascular service, including:

- Operations offered/not offered
- Thresholds for offering admission/intervention
- Seniority and/or number of specialists performing caseload
- Management of screening programmes
- Imaging availability
- Interventional radiology support and availability
- Conduct of multi-disciplinary meetings
- Changes to trainee and consultant rotas

- Surgeons' commitments and clinic availability
- Use of the vascular team members to cross cover other specialties

This information will be fed back to the VSGBI (and other relevant bodies) to allow real-time feedback on practicalities of the new guidelines. This could support adaptations needed to support best practice for patients and surgeons as the situation progresses.

## Tier 2 - Vascular and endovascular procedural data capture

## **Primary objective**

This tier of the project is aimed at capturing data on all vascular and endovascular interventions being undertaken throughout the COVID-19 pandemic. It is anticipated that the type and nature of vascular procedures performed will change due to the pressures on the wider healthcare service and rationing of resources or in-patient beds.

#### **Methods**

This will be undertaken for a 3 month period in the first instance. These time periods are subject to change depending on how the pandemic progresses.

#### **Outcomes**

## **Primary outcome:**

To document all vascular surgery and interventional procedures performed throughout the COVID-19 pandemic across participating centres; during this stage we will only collect the name of the procedure performed, time and date, with intra-operative details; no patient-specific information will be collected as part of this.

Specifically, we will collect the following information using a remote purpose built data collection form (per centre/patient):

- Type of procedure performed
- Time taken from presentation to the surgical team to intervention
- Mode of referral (primary vs. secondary care)
- Site of surgery hub or spoke hospital
- Imaging modalities used and timings
- Emergency classification i.e. urgent/emergency/elective
- Operative technique(s) and device(s) used
- Mode(s) of anaesthesia (local, regional, general, locoregional, other)
- Whether suspected or confirmed COVID-19 positive (+ve) at time of surgery, COVID-19 +ve after surgery, or COVID-19 negative (-ve)

• Documentation of changes to usual practice for this specific procedure as per surgeon's standard protocol (type of procedure, type of anaesthetic, post-procedural destination)

These **secondary outcomes** will be collected after surgery has been performed at 3, 6, and 12 months:

- Re-admission
- Re-intervention
- All-cause mortality
- Operation-specific morbidity
- Morbidity
- [If COVID-19 +ve] respiratory outcome, admission to intensive care unit.

Each centre will assign a unique patient-specific and study-specific number to each procedure/patient (kept in local site files in the NHS institutions) and then this information will be collected locally three and six months after surgery has taken place. This will be uploaded anonymised on the data collection tool.

## Tier 3 - Changes to acute vascular care management

## **Primary objective**

To identify how the management of all referred urgent vascular cases changes throughout the COVID-19 pandemic. This is to identify the many anticipated deviations from pre-pandemic best practice or pre-defined standards for acute/urgent cases due to healthcare pressures. This will focus on chronic limb-threatening ischaemia, symptomatic carotid disease, acute aortic syndromes and aneurysmal disease.

#### **Methods**

This will take place over a minimum of one month and will invite vascular specialists to complete an anonymised proforma for every patient with any of the conditions listed above, referred to the vascular service. Timings might change based on the duration of the pandemic.

#### **Outcomes**

## **Primary outcome:**

To document any deviation from "best vascular practice" and the impact on patient care, specifically focussing on:

## **Chronic Limb Threatening Ischaemia (CLTI):**

- Decision to discharge / admit / refer to hot clinic
- Decision for endovascular or open surgery first
- Decision for best medical therapy or palliation or primary amputation

#### Symptomatic carotid disease

- Number of patients managed with best medical therapy (BMT)
- Modifications to the indication and decision for carotid endarterectomy (CEA)
- Delays to treatment due to lack of theatre/bed availability

## Abdominal Aortic Aneurysm (AAA)

- Increasing use of Endovascular repair (if applicable)
- Changes to criteria for intervention
- Decisions for palliation, i.e. 'turn down'

## **Acute Aortic syndrome (AAS)**

- Decision to manage in non-critical care beds
- Changes to imaging protocol at unit level
- Decision to defer surgery

## **Secondary Outcomes:**

To collect longitudinal data to identify condition-specific outcomes for these patients at 3, 6 months and 1 year.

- Example condition specific outcome measures to include:
- CLTI limb salvage, amputation free survival, all-cause mortality
- Carotid disease ipsilateral stroke rate, any stroke rate, all-cause mortality
- AAA aneurysm-related mortality, all-cause mortality
- AAS complication rate including ruptures, all-cause mortality.

#### 7.1 Recruitment

In UK centres, patients will be recruited by a GCP trained VERN doctor or nurse in each vascular centre and then consented as per GCP guidance. A written informed consent form for tier 2 will be kept at each site file locally.

Anonymised information on participants will be collected using a remote case report form.

#### 7.1.1 Patient identification

Patients will be identified daily via conversation with the on call registrar and consultant for vascular surgery.

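### Tier 3 is meant to cover every listed case referred to the vascular service, but the identification rules reach patients only at surgery or through the on-call team, so non-operated patients entering by another route would be missed

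*Protocol*

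**What the plan says.** The Tier 3 target is wide. Its primary objective is "To identify how the management of all referred urgent vascular cases changes throughout the COVID-19 pandemic", with this scope: "This will focus on chronic limb-threatening ischaemia, symptomatic carotid disease, acute aortic syndromes and aneurysmal disease". Tier 3 Methods asks vascular specialists to "complete an anonymised proforma for every patient with any of the conditions listed above, referred to the vascular service". Section 6 makes eligible anyone assessed or treated for a vascular problem in an NHS secondary care vascular unit, with no reference to on-call.

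The case-finding rules are narrower. The opening of Section 7 covers Tiers 2 and 3 by name and gives two identification points: surgery, and "At the time of referral to the vascular on-call team". Section 7.1.1 then gives the only operational procedure: "Patients will be identified daily via conversation with the on call registrar and consultant for vascular surgery". No clinic list, meeting list or other source is named.

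Two further places bear on this. Tier 1 documents changes in "Surgeons' commitments and clinic availability" and in trainee and consultant rotas. Mode of referral (primary or secondary care) is on the Tier 2 data list, but the Tier 3 outcomes include no referral-route item.

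**The concern.** Tier 3 is about decisions. Its primary outcome includes "Decision to discharge / admit / refer to hot clinic" for limb-threatening ischaemia, as well as best medical therapy, palliation, the number of carotid patients managed medically, aneurysm turn-down and deferral of surgery. Many of these patients never reach theatre, so identification at surgery cannot find them. Under the written rules they enter Tier 3 only if they came through the on-call team.

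Three things are at stake:

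- **Counts.** A count of medically managed carotid patients depends directly on complete capture.
- **Proportions.** The denominator loses non-operated patients selectively, so the level is off even if nothing changes over time.
- **Change over time.** The objective is how management changes. If the share of urgent cases passing through on-call alters as clinics close or reopen, recorded decisions could alter for that reason as well as through real changes in care. With no route item, the two could not be separated afterwards.

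The 3-, 6- and 12-month outcomes would be collected on the same selected group.

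**Working it through.** **Step 1: the passages side by side.**

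| Question | Protocol text | Reach |
|---|---|---|
| Who should be recorded? | Tier 3 objective and Methods | All urgent listed cases referred to the service |
| Who is eligible? | Section 6 | Anyone assessed or treated in a vascular unit |
| When are they identified? | Section 7, opening (Tiers 2 and 3) | At surgery, or at referral to on-call |
| How are they identified? | Section 7.1.1 | Daily conversation with the on-call registrar and consultant |

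Patients within the first row but outside the last two are those who were not operated on and did not come through on-call.

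**Step 2: is there a figure to reproduce?** No. The Protocol does not state what share of listed referrals passes through on-call, and Section 8.1 declines any sample size calculation. What follows illustrates direction only.

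**Step 3: illustration. Every input is an assumption.** In each period there are 100 true urgent referrals: 50 more severe (70% have an intervention) and 50 less severe (30%). True interventions are 35 + 15 = 50, so the true share is 50% in both periods. The more severe group reaches on-call 90% of the time throughout. The on-call share of the less severe group, c, is varied between periods.

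*Rule as written (surgery or on-call).* All 50 interventions are found, and non-operated patients are found only through on-call:

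- Recorded N = 50 + 15 × 0.9 + 35 × c
- Recorded intervention share = 50 / recorded N
- At c = 0.3: N = 50 + 13.5 + 10.5 = 74; share = 50/74 = 67.6%
- At c = 0.8: N = 50 + 13.5 + 28 = 91.5; share = 50/91.5 = 54.6%

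Of 50 truly non-operated patients, 24 are recorded in the first case and 41.5 in the second.

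*Narrower reading of Section 7.1.1 (on-call only):*

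- Recorded N = 50 × 0.9 + 50 × c
- Recorded interventions = 35 × 0.9 + 15 × c
- At c = 0.3: 36/60 = 60.0%
- At c = 0.8: 43.5/85 = 51.2%

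| c, period 1 to 2 | Surgery or on-call: N | Share | On-call only: N | Share |
|---|---|---|---|---|
| 0.3 to 0.8 | 74 to 91.5 (+23.6%) | −12.9 points | 60 to 85 (+41.7%) | −8.8 points |
| 0.5 to 0.7 | 81 to 88 (+8.6%) | −4.9 points | 70 to 80 (+14.3%) | −3.2 points |
| 0.8 to 0.3 | 91.5 to 74 (−19.1%) | +12.9 points | 85 to 60 (−29.4%) | +8.8 points |
| 0.3 to 0.3 | no change | no change | no change | no change |

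Changes in share are computed before rounding. In the last row nothing moves over time, but the level is still wrong: 67.6% or 60.0% recorded against 50% true. If every urgent case passed through on-call, N would be 100, the share 50%, and the problem would vanish.

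**Step 4: does identification at surgery cure it?** No. It completes the numerator for interventions but leaves the non-operated part of the denominator dependent on on-call. In this model the drift in the share is larger under that rule than under on-call alone.

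**The case against.** The strongest reply is that the texts are complementary. Tier 3 Methods carries its own capture rule, addressed to vascular specialists in general. Section 7.1.1 sits under Recruitment, which is largely about consented Tier 2 patients, and does not call the on-call conversation the sole source. Tier 3 is also about acute care and urgent cases, for which on-call is a natural entry point. This would be persuasive if Section 7.1.1 stood alone. It fails because the opening of Section 7 applies the surgery and on-call time points to Tier 3 by name. The urgency limit does narrow the gap, but nothing says that every urgent listed case passes through on-call.

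A second reply is that Section 8.3 plans no comparisons. That lowers the stakes for formal inference. It does not repair an incomplete denominator, and the Tier 3 objective is itself about change.

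A reader might also infer more than the documents support:

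- *That patients are found only through on-call.* Section 7 also names the time of surgery.
- *That the recorded figures move with referral route rather than with care.* They would move with both, and route matters over time only if the on-call share shifts. Tier 1 makes that plausible, not certain. Moving a patient from clinic to on-call may itself be a change in management.
- *That specific bypass routes exist.* The Protocol does not describe urgent cases arriving through stroke services, meetings or screening without on-call contact. The hot clinic appears as a decision about a referred patient, not as an entry route.
- *That the distortion is very large.* Suppose 40 referrals come through on-call with 80% admitted and 60 through clinic with 20% admitted. The true admitted share is (32 + 12)/100 = 44%, and the on-call record reads 32/40 = 80%. After 40 clinic referrals divert, it reads (32 + 8)/80 = 50%, a fall of 30 points. No input there has a source, and sending most urgent cases through clinic is a strong assumption.

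**Conclusion.** The point holds in a limited form. The stated Tier 3 population is wider than the stated case finding, and the patients lost are the non-operated ones who enter other than through on-call. Tier 3 counts and decision proportions may therefore be incomplete, and may shift with referral route as well as with care.

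The conclusion about the text rests on the Protocol alone. A practical effect needs one assumption, that some urgent listed cases reach the service without on-call contact. A drift over time needs a second, that this share changes. The Protocol quantifies neither, so the figures above show direction and plausibility, not an estimate. The matter is worth settling before data collection because missed referrals and an unrecorded route cannot reliably be recovered later.

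**What to change.** Reconcile the opening of Section 7, Section 7.1.1, and the Tier 3 objective and Methods in one of two ways.

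1. **Widen the case finding.** State that Tier 3 cases are identified from all urgent referral routes into the service, for example hot-clinic and urgent clinic lists as well as on-call. Add one route-of-referral field to the Tier 3 proforma and report decisions by route. Cost: protocol wording, one form field, and a little extra time for the local collector.
2. **Narrow the claim.** Restate the Tier 3 population as referrals to the vascular on-call team, and limit the Tier 3 conclusions to that group. Cost: wording only. The price is that Tier 3 no longer speaks for all urgent referrals to the service.

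The first option keeps the stated objective. The second is sound if sites can cover on-call only. In either case, say which tier each identification point in Section 7 serves.
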